10.2.1 AR-Variant Studies

To determine levels of full length AR and AR-V7, blood will be obtained from patients at screening and after 2 cycles of Dex therapy. Blood samples are collected and shipped to the Johns Hopkins Laboratory within 24 hrs according to standard procedure (Appendix D).

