Treatment Plan: Patients will be prescribed Dex 2mg tablets to take daily by mouth with food. All patients will receive a minimum of two months of Dex. Following PSA or radiographic progression of disease, patients will be prescribed Enza 160 mg (40 mg tablets x4) by mouth daily. Dex will be tapered and stopped over a one week period. Enza will be continued for three months, after which time patients will be assessed for response. All patients will come off study after 3 months of Enza. Patients without evidence of response to Enza will be offered other standard of care therapy or additional clinical trial. Patients demonstrating Enza response will come off trial and be allowed to continue Enza as standard of care therapy. Blood Samples for assessment of AR and AR-V expression will be taken at baseline and at time of initiation of Enza.

Assessment of Response: Patients will have monthly PSA measurements. Disease will be assessed with bone scan and CT C/A/P at baseline, prior to initiation of Enza and at study conclusion. Progression will be defined by RECIST 1.1 and PCWG-2 criteria for soft tissue and bone metastasis, respectively. PSA response will be defined as 50% decrease in PSA from initiation of Enza. PSA progression will be defined by PCWG-2 criteria.

Rationale: The treatment options are very limited for patients with metastatic prostate cancer whose disease has become resistant to hormonal therapy and chemotherapy. Initially, the disease responds to drugs such as Enza, which block the androgen receptor. However, prostate cancer becomes resistant to this therapy through several mechanisms, including changes in the cancer's expression of the androgen receptor.

Dex and other glucocorticoids are an established treatment for prostate cancer; they can provide pain control, relief of other cancer-related symptoms like anorexia and fatigue, as well as have a direct anti-cancer effect. The receptor for glucocorticoids is expressed on many advanced prostate cancers, and recent work has theorized that there is interaction between the glucocorticoid receptor and androgen receptor pathways. It is thought that using a drug to affect one of the receptors may change the expression patterns and signaling of the other receptor.

Given that Dex has a known benefit, and that there is a likely interaction between the androgen

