- PSA response rates to Dex for patients who are AR-V7 positive and AR-V7 negative, respectively, at study entry.
- Response rates to Enza for patients who are AR-V7 positive and AR-V7 negative, respectively, at study entry.
- Percentage of patients who are AR-V7 positive at study entry who are AR-V7 negative at time of initiation of Enza, and vice-versa.

Study Scheme:

Statistical Plan:

The primary endpoint will be the PSA response rate with the re-challenge of Enza following Dex, which is defined as the proportion of subjects with a $\geq 50\%$ PSA decline from baseline and maintained for ≥ 4 weeks at any time-point after receiving Enza. The treatment regimen would be considered of insufficient activity for further study in this population if PSA response rate is 5% or less, and the minimum required level of efficacy that would warrant further study with the proposed regimen is a 25% PSA response rate. The sample size is calculated to detect an improved PSA response rate from 5% to 25%. A minimax Simon two-stage design is planned. A total of 13 patients will be entered in the first stage. If none of them show PSA response after Enza, the treatment regimen will be terminated and we will conclude the regimen is ineffective. If ≥ 1 subjects has PSA response, then additional 7 patients will be studied. If a total of 2 or fewer subjects achieve PSA response in stage one and two combined, we consider this regimen ineffective. If a total of 3 or more respond, we conclude the regimen is promising and warrant further study. The trial could be terminated early also as soon as 3 PSA responses with the post-Dex Enza treatment are confirmed.

The maximum sample size will be 20. Patients who receive at least one dose of Dex will be evaluable for PSA response. This design provides 90% power to reject a 5% PSA response in favor of 25% response rate, with a type I error of 0.1. The chance of early stopping is 0.51 when the response rate is less than 5%.

TABLE OF CONTENTS

SYNOPSIS.....	2
1. OBJECTIVES.....	8
1.1 Primary Objectives.....	8
1.2 Secondary Objectives.....	8
2. BACKGROUND	8
2.1 Study Disease.....	8
2.2 Study Agents.....	9
2.3 Study Rationale.....	11
2.4 Study Hypothesis	11
2.5 Correlative Studies Background	11
3. PATIENT SELECTION	12
3.1 Eligibility Criteria	13
3.2 Exclusion Criteria	14
3.3 Inclusion of Women and Minorities	14
4. PATIENT REGISTRATION AND ENROLLMENT PLAN.....	15
4.1 Registration Procedures	15
4.2 General Guidelines.....	15

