1.2 Secondary Objectives

- 1.2.1 Objective response rate to Enza in patients with measurable disease on CT scan using RECIST criteria.
- 1.2.2 Time to PSA progression (based upon PCWG2 criteria) for treatment with Dex.
- 1.2.3 Effect of each treatment on quality of life as assessed by patient completion of validated instruments (FACIT-Fatigue Scale, RANDSF-36) Quality of life assessments will be taken at study entry, during second on-treatment visits for both Dex and after 3 cycles of Enza.
- 1.2.4 PSA response rates to Dex for patients who are AR-V7 positive and AR-V7 negative, respectively, at study entry.
- 1.2.5 Response rates to Enza for patients who are AR-V7 positive and AR-V7 negative, respectively, at study entry.
- 1.2.6 Percentage of patients who are AR-V7 positive at study entry who are AR-V7 negative at time of initiation of Enza, or vice-versa.

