2.5 Correlative Studies Background

We will study expression of AR-V7 and its association with response to Dex and subsequent response to Enza.

The androgen receptor is a 110-kDa protein with several functional domains. Anti-androgen drugs such as Enza target the highly conserved C-terminal ligand binding domain. Transcripts that are produced by alternative splicing of the androgen receptor mRNA transcript can lead to protein products that lack the target for androgen receptor antagonists. While a total of 15

androgen receptor variants have been described, the most important variant is AR-V7. Our institution recently examined associations between AR-V7 status and PSA response rates and progression-free survival (PSA and radiographic), using multivariable cox regression analysis to determine the independent effect of AR-V7 expression on clinical outcomes.²⁴ In this study, 31 patients treated with Enza were enrolled, of which 12 (38.7%) were positive for expression of AR-V7. Patients that were positive for AR-V7 had a 0% PSA response rate to Enza compared to 52.6% for those that were negative. Other poorer outcomes similarly were associated with AR-V7 positivity including progression free survival (PSA: 1.4 vs 5.9 months; radiographic/clinical: 2.1 vs 6.1 months). The presence of AR-V7 in circulating tumor cells was found to be associated with poor response to Enza.

In preclinical cell-based prostate cancer assays performed in our laboratory, AR-V7 expressing cell-lines (VCaP and CWR22Rv1) can be growth inhibited by Dex exposure at high doses. Given that there is a previously demonstrated benefit to administration of Dex to patients with advanced disease, including PSA responses as discussed above, and there is preclinical data showing growth inhibition of cell lines, even expressing AR-V7, we will perform the correlative study to track AR-V7 expression with response Dex and Enza.

The methods have been previously described and published. Circulating tumor cells are enriched from peripheral blood collected from patients via a modified commercially available AdnaGen Prostate Cancer Select kit, wherein circulating prostate cancer cells are isolated with ligand-coated magnetic beads and lysed yielding mRNA. The cells are isolated using magnetic beads coated with 3 different antibodies (EPCAM and 2 proprietary antibodies). Quantitative RT-PCR is subsequently performed on the samples to evaluate mRNA expression of full length androgen receptor and AR-V7.

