5.2.1 Study Treatments

[figure not shown]
Patients will continue on ADT with LHRH agonist (i.e. Zoladex, Trelstar, Eligard or Lupron) or LHRH antagonist (Degarelix) if not surgically castrated throughout the duration of the study.

Patients will be prescribed Dex 2mg tablets to take once daily orally with food for 28 days/cycle continuously. Patients who have PSA progression after one cycle will continue on Dex for a second cycle. Patients with continued increase in PSA (if satisfies progression based upon PCWG2 definition) will begin Enza. Patients with declining PSA after 2 cycles of Dex will continue on Dex until PSA progression. Every 3 cycles patients will have repeat bone/CT scans to evaluate treatment response. Patients will remain on treatment with Dex until evidence of PSA progression (per the PCWG2 definition) or disease progression on CT scan (per RECIST criteria), or progressive bone metastatic disease (per the PCWG2 definition).

At time of progression, Dex will be stopped via a rapid taper over one week if patients were treated for >30 days. Patients will be instructed to take 1 mg Dex for 7days, then stop. However, ongoing use of corticosteroids will be allowed if indicated for bone pain or adrenal suppression.

Patients will then be prescribed Enza 40 mg tablets and instructed to take 4 tablets per day orally with or without food for 28 days/cycle continuously. Dose adjustments and delays will be allowed as per standard of care with treatment with Enza. Patients will have PSA checked monthly. All patients will remain on Enza for 3 cycles regardless of PSA response. At the end of 3 cycles of Enza all patients will come off study. Those patients with PSA or radiographic progression will come off study and be offered standard of care or another clinical trial. Those patients with PSA or radiographic response after 3 cycles will be offered to remain on Enza as standard of care therapy.

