5.4 Criteria for Removal from Study

A patient may be removed from the study for a variety of reasons, including:

1. As defined by the protocol, evidence of disease progression based on radiographic progression or worsening symptoms while on Enza.
2. Unacceptable adverse events
3. Intercurrent illness that prevents further participation
4. Experiencing a treatment delay of longer than 2 weeks due to drug toxicity attributed to Dex. Patients who experience treatment delay while on Enza will remain on study as per protocol.
5. Patient refuses further treatment through the study and/or withdraws consent to participate
6. Need for “stress dose” glucocorticoids due to a life threatening medical condition.
7. Patients is noncompliant with respect to taking drugs, keeping appointments, or having tests required for the evaluation of drug safety and efficacy
8. General or specific changes in the patient's condition that render the patient unacceptable for further treatment in this study in the judgment of the investigator
9. Under no circumstance will care of a withdrawn patient be adversely affected by a decision to withdraw or be withdrawn from the study.
10. Ongoing response after 12 cycles of dexamethasone.

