6.2 Treatment Period

Patients will have continuous treatment of outpatient therapy. Patients who are not surgically castrated will continue to receive ongoing GnRH agonist or antagonist therapy as prior. Patients will be assessed every 1-3 cycles at a clinic visit.

6.2.1 Cycle 1 Day 1 visit:

- Physical exam, including weight, ECOG performance status, vital signs
- CBC (Complete blood count) with differential and platelet count (Not needed if performed within the last 2 weeks at screening)
- CMP (Comprehensive Metabolic Panel - Sodium, Potassium, Chloride, BUN, Serum Creatinine, Calcium, Total Protein, Albumin, Total Bilirubin, AST, ALT, Alkaline Phosphatase, HCO₃) (Not needed if performed within the last 2 weeks at screening)
- Serum PSA
- Hemoglobin A1 (Not needed if performed within the last 2 weeks at screening)
- Blood drawn for to assess level of full length and androgen receptor variant in circulating tumor cells (CTC AR-V7)

- Quality of life surveys (FACIT-Fatigue Scale, RANDSF-36)

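### Section 10.2.1 times the second AR-V7 sample after two Dex cycles, but the rest of the protocol and the conversion endpoint need it when Enza starts

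*Protocol*

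**What the plan says.** Section 10.2.1 (AR-Variant Studies) states that "blood will be obtained from patients at screening and after 2 cycles of Dex therapy".

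The other places in the protocol that time these samples agree with one another and differ from 10.2.1:

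- The Treatment Plan in the synopsis, and footnote 7 of the study calendar (Section 9): "Blood Samples for assessment of AR and AR-V expression will be taken at baseline and at time of initiation of Enza".
- Section 6.2.2 places the second research draw at progression on Dex and equates that with the start of Enza.
- The AR-V7 row of the calendar is marked under Dex C1 and under the post-Dex progression visit. It has no mark under Dex C2 or C3.
- Section 6.2.1 lists the first draw among the Cycle 1 Day 1 procedures.

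The endpoint that uses the second sample is objective 1.2.6: "Percentage of patients who are AR-V7 positive at study entry who are AR-V7 negative at time of initiation of Enza, or vice-versa". The synopsis gives the same endpoint with the same reference time.

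Section 12.3 and the SAP report response by AR-V7 status at entry. Neither gives a draw time or an analysis of conversion, so neither settles the question.

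**The concern.** The conversion endpoint compares AR-V7 status at entry with status when Enza begins. A sample taken at a fixed time on Dex supplies the second value only if the patient changes drug at that time. For anyone who stays on Dex longer, the 10.2.1 sample is an on-Dex value and not the one the endpoint names. The right sample cannot be recovered once Enza has begun.

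The loss would also be selective, since it falls on patients with longer Dex exposure. Section 5.1 lists change in AR-V7 positivity resulting from Dex as a secondary objective. If the two sites worked from different sections, the pooled result would mix week-8 values with Enza-start values. Section 10.2.1 is also where a coordinator would naturally look: it is the section on the AR-variant studies, it refers to Appendix D for collection and shipping, and Appendix D gives no time points.

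**Working it through.** The plan states no figure on this point, so there is none to reproduce. The check compares the sampling times and asks for whom they differ.

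**Sampling times**

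| Source | First draw | Second draw |
|---|---|---|
| 10.2.1 | Screening | After Dex cycle 2 |
| Synopsis, Treatment Plan | Baseline | Start of Enza |
| 6.2.1 and 6.2.2 | Cycle 1 Day 1 | Progression on Dex / start of Enza |
| Calendar row and footnote 7 | Dex C1 (baseline) | Post-Dex progression / start of Enza |
| Endpoint 1.2.6 | Study entry | Start of Enza |

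**When the second draws coincide.** Cycles are 28 days, so the 10.2.1 draw falls at 2 × 28 = 56 days, or week 8. Section 5.2.1 has a patient whose PSA progresses after cycle 1 take a second cycle, then start Enza if the continued rise meets the PCWG2 definition. For that patient the two times agree.

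**When they do not.** Section 5.2.1 also says: "Patients with declining PSA after 2 cycles of Dex will continue on Dex until PSA progression". A patient whose PSA rises by less than the progression threshold stays on Dex as well. The cap is item 10 of Section 5.4, which removes patients for "Ongoing response after 12 cycles of dexamethasone", that is, at 12 × 28 = 336 days. The gap between the two draws can therefore approach 336 − 56 = 280 days. Patients removed under item 10, like all others who never start Enza, have no Enza-start status under either schedule and are not part of the loss.

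The PSA row of the Appendix E table counts progression without a prior decline only from week 12 (84 days, 3 cycles). Read that way, some patients with no decline would also still be on Dex at week 8. This is supporting only: Appendix E says its table does not replace the protocol, and Section 10.1 carries no 12-week condition.

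**Possible size, as an illustration.** Assumptions: every site follows 10.2.1 alone; all 20 patients start Enza; the share still on Dex after week 8 equals the range of Dex PSA response rates in Table 1 (26% to 62%); AR-V7 positivity at entry is as in Section 2.5 ("31 patients treated with Enza were enrolled, of which 12 (38.7%) were positive for expression of AR-V7"); and Dex duration is unrelated to AR-V7 status.

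- Without Enza-start status: 20 × 0.26 = 5.2 to 20 × 0.62 = 12.4.
- Entry status: 20 × 12/31 = 7.7 positive; 20 − 7.7 = 12.3 negative.
- Lost among those positive at entry: 7.7 × 0.26 = 2.0 to 7.7 × 0.62 = 4.8.
- Lost among those negative at entry: 12.3 × 0.26 = 3.2 to 12.3 × 0.62 = 7.6.

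If 6.2.2 or the calendar is followed, the loss is 0.

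**First draw.** Screening falls within the 28 days before Cycle 1 Day 1. Both times precede Dex, and either gives an entry status.

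**The case against.** The strongest reply is that the operative schedules all agree. The visit section, the calendar row and its footnote put the second draw at the start of Enza, and the endpoint names that time itself. Section 11.8 requires sites to follow the protocol as written. A site that obeyed every section would take the Enza-start sample and, at most, one extra at cycle 2. Nothing in 10.2.1 cancels the 6.2.2 draw. Section 11 adds a monthly review that covers adherence and data completeness. The endpoint is descriptive, has at most 20 patients, and is absent from the endpoint list in Section 12.1.

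Most of this stands, and it is why the point is minor. It lowers the chance of loss but does not remove the contradiction, and a review that finds a missing sample after Enza has begun cannot restore it.

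The objection to the patient counts is also fair. Staying on Dex requires a declining PSA, or no qualifying progression, and not a 50% fall. Table 1 does not describe men already treated with Enza. The counts are therefore neither an estimate nor a bound: smaller declines would raise them, and patients who never start Enza would lower them. The finding does not need them. The first-draw discrepancy has no evident analytic consequence and matters only because it sits in the same sentence.

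**Conclusion.** The inconsistency is real. Section 10.2.1 is the outlier against the synopsis, 6.2.2, the calendar and endpoint 1.2.6, and Section 5.2.1 is enough to show that the two times differ for some patients.

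Only the conversion endpoint is exposed. The primary endpoint and the Simon design rest on PSA response to Enza, and the AR-V7 response comparisons use entry status, so none of these changes.

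The number of patients affected cannot be determined from the documents. It is zero if 6.2.2 or the calendar governs in practice. If 10.2.1 alone governs, it is the unknown share of patients who start Enza after week 8; the 5 to 12 of 20 above only illustrates that share under the listed assumptions. The sentence should be corrected because it is an operative sampling instruction, the sample it could cost is irrecoverable, and the loss would be selective.

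**What to change.** Reword the sentence in Section 10.2.1 so that the first draw is at Cycle 1 Day 1 and the second at progression on Dex / start of Enza. It then matches 6.2.1, 6.2.2, the calendar and 1.2.6. If a sample after cycle 2 is also wanted, list it as an additional draw in both 10.2.1 and the calendar, so that it cannot be taken as a substitute for the Enza-start sample.

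The basic correction is one sentence and adds no blood draws; the optional cycle-2 sample would add one. Section 11.6 requires protocol changes to go through an amendment with IRB approval, so that administrative step is part of the cost.

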11. DATA REPORTING / REPORTING REQUIREMENTS

Data and safety monitoring will follow SKCCC Data and Safety Monitoring Plan. Additionally, scheduled meetings will take place monthly and will include the protocol principal investigator, research nurse, data manager, and, when appropriate, the collaborators, sub-investigators, and biostatistician involved with the conduct of the protocol.

During these meetings the investigators will discuss matters related to: safety of protocol participants, validity and integrity of the data, enrollment rate relative to expectation, characteristics of participants, retention of participants, adherence to protocol (potential or real protocol violations), data completeness, and progress of data for secondary objectives. This is a DSMP Level I study under the SKCCC Data Safety Monitoring Plan (12/6/2012). The Clinical Research Office will perform an audit after the first subject has been treated and then periodically depending on the rate of accrual and prior audit results. All trial monitoring and reporting will be reviewed annually by the SKCCC Safety Monitoring Committee. The PI is responsible for internally monitoring the study. Data must be reviewed to assure the validity of data, as well as, the safety of the subjects. The PI will also monitor the progress of the trial, review safety reports, and clinical trial efficacy endpoints and to confirm that the safety outcomes favor continuation of the study.”

11.1 Adverse Event Monitoring and Reporting

An Adverse Event is defined as any unfavorable and unintended sign (including an abnormal laboratory finding), symptom or disease temporally associated with the use of a medical treatment or procedure regardless of whether it is considered related to the medical treatment or procedure (attribution of unrelated, unlikely, possible, probable, or definite). The PI and/or the research nurse will monitor each patient closely for the development of adverse events and toxicities and record all such events. Patients will be evaluated for toxicity if they have received one dose of Dex. The timely reporting of adverse events (including toxic deaths) is required by the Food and Drug Administration (FDA).

11.2 Evaluating Adverse Events

The grade and severity of the event will be determined using the DCT/NCI Common Terminology Criteria, CTCAE v.4.0. Links to CTCAE version 4.0 can be found in Appendix B. All appropriate treatment areas should have access to a copy of the CTCAE version 4.0. Study staff must use one of the CTCAE criteria to define the event. Adverse events not included in the CTCAE v.4.0 should be reported and graded under the “Other” adverse event within the appropriate category and grade 1 to 5 according to the general grade definitions, mild, moderate, severe, life-threatening, fatal or disabling, as provided in the CTCAE.

The event will be determined to be expected or unexpected.

The event will be evaluated for relationship to the medical treatment or procedure. The Investigator should document his/her opinion of the relationship of the event to study medication as follows:

- Unrelated- The adverse event is clearly not related to the investigational agent(s).
- Unlikely- The adverse event is doubtfully related to the investigational agent(s).
- Possible- The adverse event may be related to the investigational agent(s).
- Probable- The adverse event is most likely related to the investigational agent(s).
- Definite- The adverse event is clearly related to the investigational agent(s).

Based on this information, a decision will be made whether an adverse event should be reported as an expedited report (Serious Adverse Event, section 3.0) in addition to the routinely reported clinical data. All expedited adverse event reports should be submitted to the JHM Institutional Review Board (IRB) and to the FDA.

